The primary endpoint is the prognostic value (i.e. c-statistic including confidence intervals) of the MAFA ratio with respect to full aneurysm occlusion (i.e. using the Raymond-Roy Occlusion Classification I on standard-of-care head imaging) 12 months after Flow Diverter Stent placement. Secondary endpoints are the prognostic value (i.e. c-statistic including confidence intervals) of the MAFA ratio with respect to full aneurysm occlusion on standard-of-care head imaging 6 months after flow diverter placement, the optimal threshold for the MAFA ratio and the number of adverse events.
Main inclusion criteria

 
• Subject with unruptured, <math>\geq 5</math>mm saccular aneurysm(s) located in the anterior intracranial circulation and suitable for an endovascular treatment with a Flow Diverter Stent
 
• Subject is 18 years of age or older, or of legal age to give informed consent per state or national law
 
• Subject is available for clinical follow-ups
 

Main exclusion criteria

 
• Non-saccular brain aneurysm(s) (i.e., dissecting, fusiform, atherosclerotic, mycotic, bifurcational) Prior aneurysm treatment with either endovascular (stenting, coiling) or surgical (clipping) techniques
 
• Endovascular treatment assisted with coils or intracranial stents
 
• Significant or severe allergy to intra-arterial contrast medium uncontrolled by pre-procedure medications
 
• Severe kidney disease (e-GFR < 60)
 

Philips IGT Systems  Status: Approved	Post-Market Clinical Study Plan  CARO A multicenter observational cohort study	XCY610-130253 2018 Apr 06 Revision: 2.0 Page 6 of 23
--	---	---

- Subjects not willing (or able) to attend post FDS insertion standard-of-care follow up clinic visits requiring DSA, head MRI or CTA imaging
- Subject participates in a potentially confounding drug or device trial during the course of the study.
- Subject meets an exclusion criteria according to national law (e.g. age, pregnant woman, breast feeding woman)

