#### Follow-Ups (6 and 12 months)

All registry patients treated with FDS are expected to follow their routine post treatment clinical visits, which will include a standard-of-care head imaging (e.g. CTA, MRA and/or DSA) test to classify aneurysm occlusion (i.e. Raymond-Roy Occlusion Classification I (Roy *et al.*, 1997)) at 6 months ( $\pm 49$  days) and 12 months ( $\pm 49$  days). During the 6 and 12 month follow up visits, patient medical charts will be accessed to collect adverse events (if applicable) and document any post-treatment neurological deterioration (neurological assessment, mRs scale). De-identified data (i.e. clinical notes, imaging reports etc.) will be entered in the relevant e-CRF sections.

Follow-up visit	Start visit window (days post-procedure)	Target date (days post-procedure)	End visit window (days post-procedure)
6-months	134	183	225
12 months	316	365	414

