##### Index Procedure and Discharge

The investigator will proceed with standard of care procedures on the day of Index Procedure (i.e. FDS insertion) for the target aneurysm(s). Then, endovascular treatment procedure details should be provided under the "INDEX PROCEDURE & DISCHARGE" field for each eligible patient.

Blood flow velocity will be calculated using the dedicated software AneurysmFlow (Philips Healthcare, Best, The Netherlands), which will be installed on standard of care imaging equipment. For this purpose, digital subtraction angiograms will be acquired during the procedure; just before and right after placement of the FDS.

Calculation of blood flow velocity will be performed automatically on the AneurysmFlow software. The operator will have access to the results of the calculation in addition to all of the regular information that is at his/her disposal during routine clinical practice. There are no additional devices or medications required for the study. The AneurysmFlow software uses standard-of-care 2D DSA and 3D-RA image sequences to determine this flow information. All raw image sequences will be stored for future reference.

Figure 1 shows the workflow for using the AneurysmFlow software in this study.

In step 1 a 3D rotational angiogram (3D-RA) will be performed in the neuro-interventional suite with the x-ray C-arm to acquire a 3D image volume of the aneurysm anatomy to be treated. From this 3D-RA, an optimal viewing angle for the C-arm will be determined to obtain good flow information. This angle should show the parent artery, aneurysm neck and aneurysm itself clearly without any overlap. The 3D-RA will also help to determine a good C-arm viewing angle to help position and deploy the FDS across the aneurysm.

In Step 2 a 2D DSA x-ray run with contrast agent injection (i.e. advised injection rate 1.5 to 2 cc/s) will be acquired at the optimal C-arm viewing angle determined by the 3D-RA scan to obtain dynamic blood motion information before FDS deployment at the location of the aneurysm. If the initial contrast agent injection was insufficient, the injection will be altered and repeated with another DSA run to obtain high quality image information. The FDS will then be placed at the location of the aneurysm.

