In Step 3, after FDS deployment, a second DSA run with contrast agent will be acquired (i.e. injection rate  $\approx$ 1.5 to 2 cc/s) at the optimal C-arm viewing angle determined from the 3D-RA to qualitatively evaluate blood motion in the region of the aneurysm after deployment of the FDS. The C-arm angle and injection rate of this second DSA run (post FDS deployment) must be the same as the first DSA run (pre FDS deployment). The 2 DSA runs and the 3D-RA image volume will automatically be sent to the AneurysmFlow workstation right after they are acquired. If the FDS is ballooned after placement, the physician is asked to repeat Step 3 after ballooning.

In Step 4 a routine VasoCT scan, which is another 3D rotational x-ray C-arm scan, will then be performed with the x-ray C-arm in the neuro-interventional suite to evaluate the 3D apposition of the deployed FDS with respect the vessel wall.

The region of interest around the aneurysm and the corresponding arterial segment from which it has developed will be automatically segmented by the AneurysmFlow software, but manual controls are available in the software if modifications to the anatomical segment of interest are desired by the interventionalist. These modifications can be performed by an appropriately trained study member. The software will then automatically calculate the flow parameters of the aneurysm both before and after FDS deployment, along with the MAFA ratio.

For this study, the operator will have the choice of selecting which target aneurysms are amenable to FDS treatment. Patients that have single or multiple target aneurysms that are suitable for FDS treatment as a first treatment step would be acceptable for this study. Each target aneurysm in the patient will have a separate CRF sub-form to fill out. Additionally, each target aneurysm sub-form can be further divided into several FDS sub-forms to account for multiple flow diverters, if needed. To summarize, if the patient has more than one target aneurysm and/or needs more than one flow diverter per aneurysm, then a sub-form on the CRF will need to be filled out for each aneurysm and for each FDS used.

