As shown in Figure 1, if a target aneurysm is treated with a FDS (or more than one) initially, and is then treated using another approach (such as coiling) then this target aneurysm can remain included as part of the study. However, if a target aneurysm is treated using a non-FDS approach initially (such as with coiling), followed by placement of an FDS or other approach, then the aneurysm will be excluded from the study.

Philips IGT Systems  Status: Approved	Post-Market Clinical Study Plan  CARO  A multicenter observational cohort study	XCY610-130253 2018 Apr 06 Revision: 2.0 Page 15 of 23
--	---	--

The MAFA ratio will be calculated after the placement of each FDS. For each FDS, this ratio will be determined with the flow information before any stents were placed and also with the flow information after each FDS was placed. The final MAFA ratio will be calculated using the flow information before any FDS devices were placed and using the flow information after the last FDS was placed. Clinical and imaging outcomes of a procedure will be assessed using a combination of the flow metrics calculated by the AneurysmFlow software available to the operator during interventional treatment in addition to information that is routinely acquired during FDS placement. This information acquired across the patient population in the study will also contribute to determine more precise MAFA ratio thresholds to improve prediction of complete aneurysm occlusion after FDS placement. This study will not make any recommendation on patient management or on treatment strategy. Also, this software will not disrupt standard-of-care workflow for the interventionalist.

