#### Follow-Ups (6 and 12 months)

All registry patients treated with FDS are expected to follow their routine post treatment clinical visits, which will include a standard-of-care head imaging (e.g. CTA, MRA and/or DSA) test to classify aneurysm occlusion (i.e. Raymond-Roy Occlusion Classification I (Roy *et al.*, 1997)) at 6 months ( $\pm 49$  days) and 12 months ( $\pm 49$  days). During the 6 and 12 month follow up visits, patient medical charts will be accessed to collect adverse events (if applicable) and document any post-treatment neurological deterioration (neurological assessment, mRs scale). De-identified data (i.e. clinical notes, imaging reports etc.) will be entered in the relevant e-CRF sections.

Follow-up visit	Start visit window (days post-procedure)	Target date (days post-procedure)	End visit window (days post-procedure)
6-months	134	183	225
12 months	316	365	414

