#### Endpoint

Philips IGT Systems  Status: Approved	Post-Market Clinical Study Plan  CARO A multicenter observational cohort study	XCY610-130253 2018 Apr 06 Revision: 2.0 Page 17 of 23
--	---	--

The primary endpoint is the prognostic value (i.e. c-statistic including confidence intervals) of the MAFA ratio with respect to full aneurysm occlusion (i.e. Raymond-Roy Occlusion Classification I (Roy *et al.*, 1997) on standard-of-care head imaging) 12 months after flow diverter placement.

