#### Presentation format

The primary endpoint will be presented using an ROC curve including the c-statistic and confidence intervals.

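### The plan neither names who assigns the Raymond-Roy class nor keeps the MAFA ratio from that person, so review bias in the c-statistics is possible, though not shown

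*Combined protocol and SAP*

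**What the plan says.** **Outcome definition.** The Summary defines full occlusion "using the Raymond-Roy Occlusion Classification I on standard-of-care head imaging". Section 5.4 (Endpoint) makes the primary endpoint the prognostic value "of the MAFA ratio with respect to full aneurysm occlusion (i.e. Raymond-Roy Occlusion Classification I", assessed at 12 months. Section 5.5.1 repeats this at 6 months. No flow measurement enters any of these definitions.

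**How the outcome is obtained.** In the Follow-Ups text (Summary and Section 4.4), routine CTA, MRA and/or DSA serves as the "test to classify aneurysm occlusion". Section 4.4 adds: "De-identified data (i.e. clinical notes, imaging reports etc.) will be entered in the relevant e-CRF sections". Neither place says who assigns the class.

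**Who sees the marker.** Section 4.4 (Index Procedure and Discharge) states: "The operator will have access to the results of the calculation".

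**The sentence at issue.** The same heading, in the Summary and in Section 4.4, says: "Clinical and imaging outcomes of a procedure will be assessed using a combination of the flow metrics calculated by the AneurysmFlow software". The sentence goes on to specify metrics that the operator has during treatment, together with information routinely gathered while the stent is placed.

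**What is reported.** Section 5.4 (Presentation format): "The primary endpoint will be presented using an ROC curve including the c-statistic and confidence intervals". Section 5.5.2 takes the optimal threshold from ROC analysis as well.

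The available text of the monitoring, statistics and data management sections mentions no blinding, masking, central reader or core laboratory.

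**The concern.** The study's main result is the agreement between a marker and an outcome, so the outcome has to be graded without knowledge of the marker. Grading from a mix of routine modalities may leave some scans open to judgement. If those scans are read in the light of the MAFA ratio, part of the agreement is built in by the reader. The 12-month c-statistic, the 6-month c-statistic and the threshold can all shift.

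Such a shift is systematic. More subjects do not reduce it, and the reported confidence interval does not show it. If the plan does not require the grader's role to be recorded, a reader of the final report may be unable to judge whether it could have occurred.

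**Working it through.** **1. The passages side by side**

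| Question | Where | Answer in the plan |
|---|---|---|
| What defines occlusion? | Summary; 5.4; 5.5.1 | Raymond-Roy class I on follow-up imaging; no flow input |
| Who assigns the class? | 4.4 Follow-Ups | Not stated |
| Who sees the ratio? | 4.4 Index Procedure | The operator |
| Is the ratio kept from the grader? | Whole available text | Not stated |
| Are flow metrics used to assess imaging outcomes? | Summary and 4.4 Index Procedure | Yes if read literally; probably meant as relating flow to outcome |

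**2. The plan's own sample size, and the standard error**

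Inputs from Section 5.1: θ = 0.70, κ = 0.25, α = 0.05 (one-sided, as z_α is defined there), power 0.90.

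- A = 0.5244 × 1.414 = 0.7415, so A² = 0.5498.
- V = 0.0099 × e^(−0.2749) × [10.749 + 8.5498/0.25] = 0.338.
- n_D = [1.645 × √(0.0792 × 5) + 1.2816 × √0.338]² / 0.2² = 79.2. This rounds to 80 occluded plus 20 non-occluded, or 100, as stated.
- SE at 0.70 = √(0.338/80) = 0.065. Simulation at n = 100 gave 0.066 at 0.70 and 0.074 at 0.50.

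**3. Grader who follows a cut-off (assumption)**

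The documents give neither the share of equivocal scans nor how often a reader would follow the ratio. Let f be the equivocal share, p the share of those reads that follow the ratio, and g = f × p. A read that follows the ratio is graded non-occluded if the ratio is in its worst fifth, and occluded otherwise. This keeps the 80/20 split. Equivocal scans are taken to be unrelated to the ratio, and all other grades to be correct.

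The group graded occluded is then a mixture: (1 − g) truly occluded and g from the better four fifths of the ratio. The group graded non-occluded is (1 − g) truly non-occluded and g from the worst fifth. Comparing the two mixtures gives

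AUC read = (1 − g)²θ + g(1 − g)(1 + θ) + g² = θ + g(1 − θ).

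The factor (1 + θ) is the sum of two probabilities: that a truly occluded case beats the worst fifth, and that the better four fifths beat a truly non-occluded case. It is exact when the cut matches the 80/20 split.

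| f | p | g | True 0.50 reads | True 0.70 reads |
|---|---|---|---|---|
| 5% | 25% | 0.0125 | 0.506 | 0.704 |
| 5% | 100% | 0.05 | 0.525 | 0.715 |
| 10% | 25% | 0.025 | 0.513 | 0.708 |
| 10% | 100% | 0.10 | 0.550 | 0.730 |
| 20% | 25% | 0.05 | 0.525 | 0.715 |
| 20% | 100% | 0.20 | 0.600 | 0.760 |

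A binormal simulation gives the same values to within about 0.001.

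**4. Grader with no cut-off who only leans (assumption)**

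Take f = 10%, with 20% of the influenced reads graded non-occluded on average and the odds of that grade multiplied by 2 or 3 per SD of worse ratio. By simulation, for p = 25%, 50%, 100%:

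- True 0.50 reads 0.505, 0.510, 0.518 (odds 2) or 0.507, 0.513, 0.527 (odds 3).
- True 0.70 reads about 0.699 throughout (odds 2) or 0.701, 0.703, 0.707 (odds 3).

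**5. Effect on inference**

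With an uninformative marker, n = 100, f = 10% and the cut-off grader, the two-sided 95% DeLong interval lies wholly above 0.5 in 4.5%, 6.2% and 11.2% of 20,000 simulated studies (p = 25%, 50%, 100%). Without bias the figure is 3.1%.

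**The case against.** **The sentence is loose wording.** It stands under the index procedure heading, limits its inputs to procedure-day data, and names no follow-up scan, Raymond-Roy class or grader. The sentence after it concerns thresholds that improve prediction. The endpoint definitions elsewhere are consistent and based on imaging alone. This largely stands. A reader might infer that the plan builds flow metrics into the outcome; the documents do not support that. What remains is a sentence, printed twice, whose literal meaning conflicts with the endpoint.

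**No one is shown to grade with knowledge of the ratio.** The grader may be a radiologist who never saw it. This stands too. A reader might infer that the c-statistic will be inflated; nothing in the documents shows that.

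**The e-CRF is not available.** Section 4.4 says that "a sub-form on the CRF will need to be filled out for each aneurysm and for each FDS used", so treatment details have a place, but whether the follow-up forms identify the grader is unknown. One can say only that the plan does not require it, not that the form lacks it.

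**The cut-off scenario is severe.** The plan states no numerical cut-off, and finding one is a secondary objective. With a leaning grader, an AUC of 0.70 hardly moves. This is fair, and is why both models are shown. The opposite inference, that the shift must be small, is not supported either: with 20% equivocal scans all following the ratio, 0.50 reads 0.60, a shift of 0.10 against a standard error of 0.074.

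**Conclusion.** The point holds as a missing safeguard and an inconsistent sentence, not as demonstrated bias. The operator has the ratio, the grader is unnamed, and nothing in the available text separates the two. The 12-month and 6-month c-statistics and the threshold are exposed.

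The size cannot be derived from the documents. Under the assumed ranges, the upward shift runs from almost nothing to 0.10 at a true AUC of 0.50 and to 0.06 at 0.70. With a leaning grader it stays below 0.03 at 0.50 and below 0.01 at 0.70. All of this rests on the assumed shares of equivocal and influenced reads and on the plan's 80/20 split. The missing workflow figure and the removed pages could not be checked.

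The change is worth making because it protects the primary endpoint at little cost. It neither calls the sample size into question nor implies that any result would be wrong.

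**What to change.** 1. In the Summary and Section 4.4 (Index Procedure and Discharge), reword the sentence so that flow metrics are related to clinical and imaging outcomes and are not used to assign them.
2. In the Follow-Ups text (Summary and Section 4.4) and the Endpoint text of Sections 5.4 and 5.5.1, add: *Raymond-Roy class at 6 and 12 months is assigned without access to AneurysmFlow results.* Comparison with earlier images stays allowed; only the flow results are withheld.
3. State that the e-CRF records whether the grader was the index operator, and report how many grades that covers.

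**Cost.** Some plan wording and, if the form does not already have it, one e-CRF item. No new reader, scan or patient procedure is needed. Withholding the results is a small added step for sites that otherwise follow normal practice. Where the index operator grades, the rule reduces the bias but cannot remove it, because the operator may remember the ratio. That is the reason for item 3. The change is best made before the first 6-month grading.

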#### Follow-Ups (6 and 12 months)

All registry patients treated with FDS are expected to follow their routine post treatment clinical visits, which will include a standard-of-care head imaging (e.g. CTA, MRA and/or DSA) test to classify aneurysm occlusion (i.e. Raymond-Roy Occlusion Classification I (Roy *et al.*, 1997)) at 6 months ( $\pm 49$  days) and 12 months ( $\pm 49$  days). During the 6 and 12 month follow up visits, patient medical charts will be accessed to collect adverse events (if applicable) and document any post-treatment neurological deterioration (neurological assessment, mRs scale). De-identified data (i.e. clinical notes, imaging reports etc.) will be entered in the relevant e-CRF sections.

Follow-up visit	Start visit window (days post-procedure)	Target date (days post-procedure)	End visit window (days post-procedure)
6-months	134	183	225
12 months	316	365	414

#### Adverse Events

All (serious) adverse events (i.e. re-operations, ruptures and deaths) whether or not related to the investigational device will be collected and reported conform local rules and regulations.

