### 5.2. General Consideration

The primary analysis of the prognostic value of the MAFA ratio for predicting full aneurysm occlusion 12 months after flow diverter placement will be performed including all subjects who underwent treatment. Baseline patient characteristics and follow-up results will be summarized descriptively using frequencies and percentages or summary statistics like means and medians (including confidence intervals and interquartile ranges). Multiple imputation methods will be used to correct for missing data (Rubin, 1987). All statistical analysis will be performed using R statistical software ([www.r-project.org](http://www.r-project.org))

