#### 5.5.3. Secondary objective: Adverse events

##### Objective

To register (serious) adverse events (i.e. re-operations, ruptures and deaths).

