##### Endpoint

Philips IGT Systems  Status: Approved	Post-Market Clinical Study Plan  CARO A multicenter observational cohort study	XCY610-130253 2018 Apr 06 Revision: 2.0 Page 18 of 23
--	---	--

The endpoint for this secondary analysis is the (total) number of adverse events.

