#### Experimental design

The number of adverse events will be described using frequencies and percentages

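### The safety endpoint counts only re-operations, ruptures and deaths, so the neurological deterioration and mRS recorded at follow-up are not part of it

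*Combined protocol and SAP*

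**What the plan says.** The secondary safety objective in 5.5.3 is "To register (serious) adverse events (i.e. re-operations, ruptures and deaths"), and 3.2 and the objectives in the Summary agree. The adverse-event paragraph in 4.4, repeated in the Summary, provides for collecting and reporting "All (serious) adverse events (i.e. re-operations, ruptures and deaths) whether or not related to the investigational device".

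Section 5.5.3 then fixes the endpoint and its analysis: "The endpoint for this secondary analysis is the (total) number of adverse events", and "The number of adverse events will be described using frequencies and percentages", shown in a table.

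For the 6- and 12-month visits, 4.4 asks for chart review to "collect adverse events (if applicable) and document any post-treatment neurological deterioration (neurological assessment, mRs scale").

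The only analysis text that could reach the neurological data is general. It stands at the opening of section 5 and again in 5.2: "Baseline patient characteristics and follow-up results will be summarized descriptively using frequencies and percentages or summary statistics like means and medians".

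**The concern.** The plan records two kinds of harm information at each follow-up visit and carries only one of them into the safety endpoint. The three listed event types describe severe outcomes and one intervention. They have no place for a lasting neurological deficit that was not fatal, did not come from a rupture and did not lead to re-operation.

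Section 2 names procedural risks and bleeding after the procedure among the open questions for flow diverters, and section 14 states the intention to publish. A published table headed as adverse events, regardless of relation to the device, would normally be read as covering such deficits. Under 5.5.3 it would not.

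**Working it through.** The plan gives no figure on this point, so the check is a comparison of the relevant texts.

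1. **Definition.** Adverse events are specified in five places: the Summary (objectives and adverse-event paragraph), 3.2, 4.4 and the objective in 5.5.3. All five give the same three items, introduced by *i.e.*, and none ends in *etc.* or another sign that the list is open.

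2. **Endpoint.** 5.5.3 counts the events so defined. The endpoint paragraph of the Summary likewise gives the number of adverse events and adds no category.

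3. **Collection.** The follow-up text in 4.4 joins two tasks with *and*: collecting adverse events, and documenting neurological deterioration by neurological assessment and mRS. The second is listed beside adverse events, not as one of them.

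4. **Use of the neurological data.** The outcome in 5.4, 5.5.1, 5.6.1 and 5.6.2 is aneurysm occlusion. 5.5.2 concerns the MAFA ratio threshold. 5.5.3 covers the three event types. None of them names mRS or deterioration. What remains is the general summary of follow-up results in section 5 and 5.2, which could include these data but does not name them and is not the safety endpoint.

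5. **Monitoring.** Section 4.5 directs monitoring to critical data that affect the endpoints and excludes data collected for other reasons. On that wording the neurological fields also go unmonitored.

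6. **Other safety text.** Section 12 covers deaths and serious injuries, but only those to which a device may have contributed, and sends them to device reporting. It does not feed 5.5.3.

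7. **What the rule does to an event.**

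| Event after treatment | In the 5.5.3 total? |
|---|---|
| Death | Yes |
| Deterioration caused by rupture | Yes, as a rupture |
| Deterioration leading to re-operation | Yes, as a re-operation |
| Non-fatal deterioration with neither | No |

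8. **Unit of count.** 5.5.3 asks for percentages of a total number of events without giving a denominator. Under 4.4 a subject may have several target aneurysms and several stents, so events and affected subjects need not be equal in number.

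9. **Baseline.** The screening text in 4.4 lists demographics, medical and surgical history, aneurysm data and imaging details. It does not name mRS, so a change in mRS cannot be assumed to be available.

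**The case against.** The strongest reply has four parts.

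**The data may still be reported.** Neurological status recorded at a follow-up visit is, on a plain reading, a follow-up result. A reader might infer from 5.5.3 that these data are never analysed. The documents do not support that, because section 5 and 5.2 provide for a descriptive summary that can include them. This limits the point to the safety endpoint and leaves it standing there.

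**The list may not be closed.** Section 4.4 elsewhere uses *i.e.* before a list that ends in *etc.*, so the abbreviation is not used strictly. But the adverse-event list appears five times with the same three items and no *etc.*, and 4.4 lists deterioration separately from adverse events. The loose usage elsewhere does not open this list.

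**The scope may be deliberate.** The device is marketed software, the study is observational, and the objective is only to register events. There is no safety hypothesis, comparator or threshold. A reader might infer that the plan would reach a flatteringly favourable safety conclusion. The documents do not support that either, since no safety conclusion is planned and no event rates are given. Still, the plan chose to make adverse events a secondary endpoint regardless of device relation, so readers need to know what the total leaves out.

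**Widening the definition has a cost.** This stands. An open-ended definition could enlarge collection, reporting and monitoring well beyond the present plan. The remedy should therefore add one named category and no more.

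**Conclusion.** The point holds as a gap in the secondary safety endpoint. A non-fatal disabling neurological event without rupture or re-operation would be documented at follow-up but left out of the reported total, and the fields that record it would not be monitored.

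The size cannot be estimated. The undercount equals the number of such events, and the documents give no rate from which to project it. The primary c-statistic, the sample size and patient procedures are not affected. The change is worth making but does not decide the validity of the study.

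The conclusion rests on reading the three-item list as complete and on the neurological item in 4.4 being separate from adverse events. A reader might also infer that change in mRS is already available. The documents show only that mRS is collected at 6 and 12 months.

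**What to change.** - In 5.5.3, with matching text in the Summary, 3.2 and 4.4, add post-treatment neurological deterioration as a named fourth event category. Keep the list closed.
- In the 5.5.3 table give, for each type, the number of events, and the number and percentage of treated subjects with at least one event. Add a row for subjects with any event, so that a subject who has both a rupture and a deterioration is counted once there.
- Report the mRS distribution at 6 and 12 months in the same table, with the number of subjects assessed. Give change from baseline only for subjects with a recorded baseline mRS, and state how many there are.

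The cost is revised wording in four places and additional rows in a table already planned, using follow-up data that 4.4 already collects. The reported event total may be higher, and the neurological fields would become endpoint data subject to monitoring under 4.5.
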